Random assignments will be made by the study statistician in permuted blocks of size 2 and 4. The block size will also be randomly generated to minimize correct prediction of assignments and preserve approximate balance between groups, using the rand function in SAS. The randomization module will be built into REDCap. Study staff (SC or RA) will enable randomization in REDCap for each participant after completion of the informed consent process and baseline data collection. If the REDCap randomization module is not available, envelopes will be used. Personnel from the Albert Einstein School of Medicine will prepare each randomization packet in a sealed envelope and send these to each site in batches. A date/signature label will be placed over the envelope seal. Randomization envelopes will be stored in locked cabinets and opened by study staff (SC or RA) after completion of the informed consent process and baseline data collection.

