6.2.2 Enrollment, Baseline, and/or Randomization

Enrollment

Subjects are considered enrolled once the informed consent document has been signed and randomization has occurred. Only one written informed consent document will be used, as we have

requested a partial HIPAA waiver for screening.

Baseline Assessments

- Pre-Treatment Pain Intensity Assessment (Pre) using a 0-10 NRS^{58,59} will be collected: a) for acupuncture patients, before administration of acupuncture; b) for usual care patients who receive a pain medication order within 60 minutes (+/- 15 minutes) of being roomed, just before or at administration of pain medication; or c) for usual care patients who have not received a medication order within 60 minutes (+/- 15 minutes) of being roomed, at 60 minutes (+/- 15 minutes). The collection time window of 60 minutes was based on median time from being roomed to first pain medication (54 minutes) using data obtained from the ANW ED pilot study (See Figure 1). Pre-treatment pain assessments will be timed to be completed immediately prior to the administration of either the acupuncture or usual care treatments.
- Anxiety scores using a 0-10 NRS^{58,59}
- Expectancy will be measured with the following questions.
 - By the end of the treatment period in the ER, how much improvement in your pain symptoms do you think will occur?
0% 10% 20% 30% 40% 50% 60% 70% 80% 90% 100%

Now, please close your eyes for a few moments and try to identify what you really feel about the treatment and its likely success. Then answer the following questions:

- At this point, how much do you really feel that the treatment will help you to reduce your pain symptoms?
1 2 3 4 5 6 7 8 9
Not at all Somewhat Very much
- By the end of your treatment period in the ER, how much improvement in your pain symptoms do you really feel will occur?
0% 10% 20% 30% 40% 50% 60% 70% 80% 90% 100%

Randomization

Immediately after screening, obtaining informed consent from eligible patients, and collecting baseline data, the study staff will randomize patients to either Acupuncture or Usual Care.

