 - 1. Several times a day
 - 2. Once a day
 - 3. Several times a week
 - 4. Once a week
 - 5. Several times per month
 - 6. Once per month
 - 7. Can't recall
 - 8. Decline to answer
 - 9. Other: [FREE TEXT]

5. Have you visited an emergency room for pain within the past 12 months?

- a. Yes
- b. No
- c. Do not know
- d. Decline to answer
 - i. If yes, how many times in the last year?
 - 1. 1

- 2. 2-4
- 3. 5-7
- 4. 11+
- 5. Decline to answer

6. Have you used any non-medication treatments for your pain?

- a. Yes
- b. No
- c. Don't know
- d. Decline to answer
 - i. If yes, what methods have you used? Please select all that apply.
 - 1. Physical Therapy
 - 2. Chiropractor
 - 3. Massage
 - 4. Exercise
 - 5. Acupuncture
 - 6. Hot / cold therapy
 - 7. Meditation
 - 8. Decline to answer
 - 9. OTHER [FREE TEXT]

7. Have you ever received acupuncture?

- a. Yes
- b. No
- c. I don't know
 - i. If yes, was the acupuncture effective to relieve your symptoms?
 - 1. Yes
 - 2. No
 - 3. Do not know
 - 4. Decline to answer

8. Please rate your confidence that non-medication treatments can reduce pain, on a 0-10 scale, where 0 is not confident and 10 is completely confident.

0 1 2 3 4 5 6 7 8 9 10 Unsure

“PRE” FORM – Patient facing, same for both arms, blinded to coordinator

INSTRUCTIONS: “There are some additional questions for you to answer on this iPad or your phone. I will be here to answer any questions you may have. Please do not show me the answers to these questions. Please hand the iPad back to me when you are done or let me know when you have completed the survey on your phone.”

SECTION 1 – Demographics Patient Facing, to be answered by the patient; blinded. Questions need to be presented as shown here in longitudinal fashion.

1. What is your date of birth?
2. What is your ethnicity?
 - a. Hispanic or Latinx
 - b. Not Hispanic or Latinx
 - c. Decline to answer
3. What is your race? Check all that apply.
 - a. American Indian or Alaska Native
 - b. Asian
 - c. Black or African American
 - d. Native Hawaiian or other Pacific Islander
 - e. White
 - f. Other [FREE TEXT]
 - g. Decline to answer
4. My sex assigned at birth is:
 - a. Female
 - b. Male
 - c. Intersex
 - d. Decline to answer
5. What is your current gender identity?
 - a. Male
 - b. Female
 - c. Trans male/Trans man
 - d. Trans female/Trans woman
 - e. Genderqueer/Gender non-conforming
 - f. Different Identity [FREE TEXT]
 - g. Decline to answer
6. How much formal education do you have?

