SECTION 4 – Anxiety

2. Please rate your anxiety, **right now**, on a scale of 0 to 10, where 0 is no anxiety, and 10 is the worst anxiety imaginable.

0	1	2	3	4	5	6	7	8	9	10
---	---	---	---	---	---	---	---	---	---	----

SECTION 5 – Randomization (logic to open up this form)

→ Build randomization module into REDCap

POST ACUPUNCTURE FORM – Patient facing, blinded to coordinator

INSTRUCTIONS: “There are some additional questions for you to answer on this iPad or your phone. I will be here to answer any questions you may have. Please do not show me the answers to these questions. Please hand the iPad back to me when you are done or let me know when you have completed the survey on your phone.”

SECTION 1 – Pain

1. Please rate your pain, **right now**, on a scale of 0 to 10, where 0 is no pain, and 10 is the worst pain imaginable.

0 1 2 3 4 5 6 7 8 9 10

SECTION 2 – Anxiety

2. Please rate your anxiety, **right now**, on a scale of 0 to 10, where 0 is no anxiety, and 10 is the worst anxiety imaginable.

0 1 2 3 4 5 6 7 8 9 10

SECTION 3 – Satisfaction

3. How satisfied are you with how your pain was managed during your ED visit?

- a. Very Unsatisfied
- b. Somewhat Unsatisfied
- c. Neutral
- d. Somewhat Satisfied
- e. Very Satisfied

4. Overall how satisfied are you with your treatment during your ED visit?

- a. Very Unsatisfied
- b. Somewhat Unsatisfied
- c. Neutral
- d. Somewhat Satisfied
- e. Very Satisfied

SECTION 4 – ED Impact (Acupuncture Arm Only)

1. Please rate the impact of acupuncture on your ED visit today.

- a. Very Negative
- b. Somewhat Negative
- c. Neutral
- d. Somewhat Positive
- e. Very Positive

POST ACUPUNCTURE FORM – Coordinator facing, information gathered from Acupuncturist

SECTION 4 – Ear Seeds (Acupuncture Arm Only)

1. Did the participant receive ear seeds in the ER
 - a. Yes
 - b. No

POST USUAL CARE FORM – Patient facing, blinded to coordinator

INSTRUCTIONS: “There are some additional questions for you to answer on this iPad or your phone. I will be here to answer any questions you may have. Please do not show me the answers to these questions. Please hand the iPad back to me when you are done or let me know when you have completed the survey on your phone.”

SECTION 1 – Pain

1. Please rate your pain, **right now**, on a scale of 0 to 10, where 0 is no pain, and 10 is the worst pain imaginable.

0 1 2 3 4 5 6 7 8 9 10

SECTION 2 – Anxiety

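### Section 6.2.2 treats Pre pain as a pre-randomisation baseline item but times it by usual-care assignment, so it cannot be carried out as written and the Pre and Post times are ambiguous

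*Combined protocol and SAP*

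**What the plan says.** Section 6.2.2 of the protocol places Pre pain under Baseline Assessments, with anxiety and expectancy, and sets its time in three items. Item a, for acupuncture, is before needling. Item b is "for usual care patients who receive a pain medication order within 60 minutes (+/- 15 minutes) of being roomed, just before or at administration" of the drug. Item c is "for usual care patients who have not received a medication order within 60 minutes (+/- 15 minutes) of being roomed, at 60 minutes", with the same 15-minute tolerance. The 60-minute limit is taken from a 54-minute median time from rooming to first pain medication in the earlier single-ED pilot, with a reference to Figure 1. The section adds: "Pre-treatment pain assessments will be timed to be completed immediately prior to the administration of either the acupuncture or usual care treatments".

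Under Randomization, the same section says: "Immediately after screening, obtaining informed consent from eligible patients, and collecting baseline data, the study staff will randomize patients". Section 4.3 says staff "will enable randomization in REDCap for each participant after completion of the informed consent process and baseline data collection", and sections 3 and 9.2 give the same order for envelopes.

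In Appendix B the PRE form is "Patient facing, same for both arms, blinded to coordinator". Pain is its Section 3, anxiety its Section 4, and randomisation its Section 5. The next pain item is on the arm-specific POST form.

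Section 6.2.4 times Post at 60 minutes, give or take 15, from Pre. Sections 3 and 5.1 say the design lets usual-care drugs take effect, and ask for acupuncture as early in the visit as possible.

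**The concern.** Items b and c need the arm to be known. The baseline heading, the randomisation sentence and the PRE form all put the score before the arm is known. Each way of resolving this has a cost.

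- If Pre follows items b and c, usual-care baseline pain is reported by a patient who already knows the allocation. The same holds for acupuncture if its Pre is taken just before needling. The Précis calls the trial un-blinded. Masking scores from staff (6.1) limits assessor influence, not patient influence.
- If Pre follows the PRE form, Post is tied to an early score and no longer tracks medication, which sections 3 and 5.1 intend it to do.

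Both ED pain change scores in section 9.5 start from Pre, and anxiety is collected with pain. Sites that resolve the conflict differently would produce scores that are not comparable, although section 9.5 describes them by site. The primary objective (1.1) is to refine procedures for the definitive trial, and this timing is one of them.

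**Working it through.** **The plan's own computed figure.** The only one is the future trial's sample size (9.2), and Pre timing does not enter it. With SDs 2.52 and 3.2, margin 0.65, one-sided 0.05 and 80% power: (2.52² + 3.2²)(1.645 + 0.842)² / 0.65² = 242.8 per arm. Dividing by the Mann-Whitney efficiency 3/π gives 254.2, so 255 per arm and 510 in total. 255/0.78 gives 327 per arm, 654 in total. Both figures reproduce and are unaffected.

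**Can one score satisfy both orders?** Item a can: a score taken before randomisation is also before needling. Items b and c can do so only if randomisation waits, for every patient, until first medication or about 60 minutes after rooming. No section prescribes that wait. It would conflict with immediate randomisation in 6.2.2 and with early acupuncture in sections 3 and 5.1. Appendix B has no second pre-treatment pain field, so a post-randomisation Pre has nowhere of its own to be recorded.

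**Timing inputs** (minutes after rooming):
- PRE = time of the PRE-form pain score; not given in the documents.
- M = time of first pain medication; 54 is the pilot median (6.2.2).
- Post = Pre + 60, range +45 to +75 (6.2.4).

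**Items b and c followed.**
- Item b, M = 54: Pre at 54; Post at 54 + 60 = 114 (54 + 45 = 99 to 54 + 75 = 129); 60 minutes on drug (45 to 75).
- Item c: Pre at 45 to 75; Post from 45 + 45 = 90 to 75 + 75 = 150.

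**PRE-form order followed.**
- Post at PRE + 60. With M = 54, time on drug is PRE + 60 − 54 = PRE + 6 (PRE − 9 to PRE + 21 across the window).
- Gap between readings for PRE up to 54: 114 − (PRE + 60) = 54 − PRE.
- Nominal Post precedes medication only if M > PRE + 60.

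**Illustration with assumed PRE times:**

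| PRE (assumed) | Post, form order | Time on drug at Post | Gap to item b |
|---|---|---|---|
| 15 | 75 | 21 | 39 |
| 30 | 90 | 36 | 24 |
| 45 | 105 | 51 | 9 |

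**Patients covered.** Two arms in blocks of 2 and 4 imply 1:1 allocation, so 150/2 = 75 usual-care patients.

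**The case against.** The best defence is that Pre was always meant to follow randomisation. Section 2.2 says the predecessor pilot collected it in that order, and section 9.2 says this trial tests the pilot's procedures. The table in 6.1 and the text of 10.2 list baseline variables apart from pain and anxiety, so baseline data in sections 3, 4.3 and 9.2 need not include Pre. On that view items a to c work as written, and only a heading and a form section are misplaced. This may well be how the conflict arose. It does not remove it: 6.2.2 itself calls Pre a baseline assessment, and the REDCap form places randomisation after it.

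Figure 1 and the Manual of Procedures could not be seen, and either may settle the order in practice. That limits certainty. Section 6.2.2 and Appendix B would still disagree.

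It is also fair that a score just before treatment, with Post an hour later, is a legitimate design giving a common interval in both arms. That stands, and the fix keeps such a score.

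A reader might infer more than the documents support:
- That usual-care Post is taken before medication. At the 54-minute median it is not.
- That less than 60 minutes on drug is too short. Section 6.2.4 calls one hour the maximum time to effectiveness.
- That only usual care would have a post-allocation baseline. Acupuncture would too if Pre is taken immediately before treatment.
- That the direction or size of a bias is known. Nothing in the documents gives either.

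**Conclusion.** The inconsistency is real and lies in operative text: section 6.2.2 conflicts with itself and with the Appendix B form order. It should be fixed, with medium confidence because Figure 1 is not available.

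The items in conflict govern all of usual care, about 75 patients. That counts patients under an unworkable rule, not patients shown to be mismeasured. The shift in Post is 54 − PRE minutes at the pilot's median. With PRE unknown, and the median taken from a different ED, no single value can be claimed.

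The consequence is limited. Section 3 names recruitment and retention as primary, and section 9.5 only describes pain change, although it calls those scores primary outcomes. What is affected is the meaning and cross-site comparability of the descriptive pain and anxiety changes, and the procedure passed to the definitive trial.

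**What to change.** 1. In 6.2.2, state that the PRE-form score is taken before randomisation in both arms and is the baseline. The REDCap form order already has this.
2. Move items a to c to a separately labelled treatment-start 0–10 score, with its own field in Appendix B.
3. In 6.2.4, state which of the two scores starts the Post clock of 60 ± 15 minutes. Treatment start keeps the stated intent on medication time.
4. Time-stamp PRE, treatment start and Post. Report the intervals by arm, and the change from both scores.
5. Make 6.2.2, Figure 1 and Appendix B agree.

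The cost is some rewording, time stamps and one extra 0–10 item. There are two real downsides if Post runs from treatment start.

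First, the PRE-to-Post interval may differ by arm. In usual care it is (54 − PRE) + 60 = 114 − PRE minutes at the median, or (60 − PRE) + 60 = 120 − PRE with no order, for PRE before those times. In acupuncture it is 60 minutes plus the wait for the session. Hence the reporting by arm.

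Second, sections 3 and 5.1 hold medication in the acupuncture arm until Post is collected. Compared with timing Post from the PRE form, analgesics could be withheld longer by the wait for the session. Ending the withholding when the session ends, as section 5.3.3 and the provider sign-off in 6.2.1 already have it, avoids this.

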6.2.3 Blinding

Data collectors in the ED will be masked to study outcomes of a given patient by use of electronic data collection methods.

6.2.4 Follow-up Visits

Post Treatment Assessment

- Post-Treatment Pain Assessment (Post) using a 0-10 NRS will be collected within 60 minutes (+/- 15 minutes) of the Pre-Treatment score, thus including the acupuncture and usual care periods. Based on pharmacokinetics of the most common pain medications used in emergency care one hour is the maximum time to effectiveness for any pain medication currently administered in most EDs.
- Anxiety scores using a 0-10 NRS will be collected at the same time as pain intensity.
- Satisfaction and will be measured through brief questions. All participants will be asked to answer:
 - "How satisfied are you with how your pain was managed during your ED visit" on the 5-point Likert scale.

- “Overall how satisfied are you with your treatment during your ED visit?” on the same Likert Scale. CI across sites as well as across patient groups such as different presenting complaints and patient demographics.

ED Discharge Assessment

ED Discharge Assessment (ED Discharge) will be obtained within 15 minutes of patients' discharge from the ED, for both acupuncture and usual care patients. If the study staff's shift has ended and it has been longer than 15 minutes since collecting post-treatment scores, study staff will collect discharge scores from the participant and leave for the day. Discharge scores will not be attempted to be collected if the participant is discharged within 15 minutes of when post treatment scores were collected. This will not be considered missing data.

- Pain Assessment (Post) using a 0-10 NRS
- Anxiety scores using a 0-10 NRS
- Satisfaction and will be measured through brief questions. All participants will be asked to answer;
 - “How satisfied are you with how your pain was managed during your ED visit” on the 5-point Likert scale.
 - “Overall how satisfied are you with your treatment during your ED visit?” on the same Likert Scale. CI across sites as well as across patient groups such as different presenting complaints and patient demographics.
- ED Impact and will be measured through a brief question given to Acupuncture patients only at ED discharge, participants will be asked to answer;
 - “Please rate the impact of acupuncture on your ED visit today.” on the 5-point Likert scale.
- All pain medications utilized in the ED will be obtained from the EHR after patient discharge.

One Week Follow-Up Assessment Visit

1 week follow-up Assessment (Follow-up) will be obtained via REDCap based text message or email (or phone call from research staff) at 1 week (+/- 4 days) of patient's ED discharge for both arms. To maintain assessor blinding, any 1-week phone calls (if needed) will be conducted by a research staff (SC or RA) who did not interact with the patient during their study participation in the ED.

- Pain Assessment (Post) using a 0-10 NRS
- Anxiety scores using a 0-10 NRS
- Satisfaction and will be measured through brief questions. All participants will be asked to answer;
 - “How satisfied are you with how your pain was managed during your ED visit” on the 5-point Likert scale.
 - “Overall how satisfied are you with your treatment during your ED visit?” on the same Likert Scale.
- Pain medications utilized from ED discharge to 1 week after discharge will be obtained from patients via phone call, email, or text messaging via the secure REDCap electronic data collection tool.

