6.2 Description of Evaluations

6.2.1 Screening Evaluation

At each ED, the Study Coordinator (SC) or Research Assistant (SC) and acupuncturist will work as a team, staffing an average 2.5, 4-6 hour recruitment/intervention sessions per week, varying the times

and days across sites as this may influence adoption. As in Figure 1, after the ED RN conducts the initial triage activity, the SC or RA (“study staff”) will identify and conduct initial eligibility pre-screening in the in the ED triage unit. The patient will then be roomed and seen by the ED clinical provider. If the ED provider determines that patient does not have a clinical condition prohibiting study participation, s/he will sign a study approval form (see below). The study staff will then approach the patient for study participation.

Provider sign off

Acupuncture in the Emergency Department for Pain Management (ACUITY)

If the patient is randomized to the acupuncture arm, please withhold pain and anxiety medications until after the acupuncture session.

The study coordinator will inform you what arm they are assigned to and when their session has ended.

In order for this patient to be eligible to participate in the "Acupuncture in the ED" study, please verify you have examined the patient and believe to the best of your knowledge, at this time, that the patient does not have the following conditions:

Critical status / Trauma
 Bone fracture
 Joint dislocation
 Migraine
 Psychological / psychiatric concern
 Clinical judgement / Other:

If you deem the patient eligible for the study, the patient will be randomized to acupuncture or usual care.

Patient can continue in study
 Patient is excluded from study

Sign: _____

Consenting Procedure

We have requested a partial HIPAA waiver for prescreening. Therefore, patients will only be consented once the screening process is over and eligibility is confirmed.

The consent process will occur after the patient has gone through the triage process and been assigned to a room within the ED. The consent process will be conducted by dedicated research staff (SC or RA) that have been trained in obtaining informed consent and who have current Human Subjects Protection and Good Clinical Practice certifications. The status and location of the patient will be monitored by

research staff using the EHR to ensure the patient is approached at an appropriate time.

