9.5 Outcomes

Implementation and Treatment Outcomes

All data analyses will be preceded by extensive data checking and verification to identify and resolve the reasons for missing values, inconsistencies, and out-of-range values. Although we anticipate little missing data based on our experience, we will carefully examine whether missingness is completely at random, at random or informative. Models proposed for analysis can handle incomplete data but do

require at least that missingness be at random. Descriptive statistics of primary outcomes: pain intensity change scores for Pre-Treatment to Post-Treatment and Pre-treatment to ED Discharge as well as secondary outcomes will be conducted to assess their distribution overall and by sites as well as demographic characteristics (e.g. sex, age group, race, household income, pain location among others). The variables will be summarized using descriptive statistics (sample size, mean, standard deviation, median, minimum, and maximum) for continuous variables and by the number and percentage of patients for categorical variables. We will report 95% exact confidence interval of median⁸³ for the key continuous variables and 95% exact binomial confidence interval⁸⁴ for categorical variables. All assessments will include sex as a biological variable as described below.

Feasibility of Recruitment and Retention

We will assess recruitment rates (# enrolled / # eligible), pace of accrual, data completeness, and retention at each data collection point, overall and across sites. We will assess variables across different patient groups (including age, race, sex), and across the study arms. Provider adoption will be assessed by the proportion of their eligible patients that clinicians approve for study participation. We will assess variables across different provider characteristics (including age, race, sex), and across the study sites. Completeness of data collection and retention at each time point: we will also track completeness of data collection, and patterns and proportions of missing data at each time point. We will compare these proportions overall and across sites and by demographics as described above.

Acceptability

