9.5.1 Primary Outcome

The primary objective of the current protocol is to conduct a feasibility RCT to examine the feasibility of refined data collection procedures, and examine intervention implementation and treatment outcomes across sites. As well as, evaluate the feasibility of research procedures, including data quality completeness, participant recruitment and retention, and using study records.

Data Completeness

Using study records and administrative data, we will track recruitment (proportion of eligible patients recruited), document recruitment rates (time to recruit intended sample), and rates of loss to follow up. Data collection forms collected at each time point will be evaluated for quality and completeness. In addition, all quantitative data analyses will be preceded by extensive data checking and verification to identify and resolve the reasons for missing values, inconsistencies, and out-of-range values. Although we anticipate some missing data based on our experience, we will carefully examine whether missingness is completely at random (MCAR), at random (MAR) or informative (MNAR). Models proposed for analysis can handle incomplete data but do require at least that missingness be at random. Modelling will consider using multiple imputation techniques of covariates to reduce potential biases.

Recruitment/Retention

To assess recruitment, we will track the number of eligible patients presenting to the ED during the time of enrolling sessions and the proportion who agree to participate. Basic demographics and presenting complaint will be collected for all eligible patients, allowing us to identify subgroups who are more or less likely to participate. Similarly approaches will be used to assess rates of loss to follow up at all data collection points. We will assess variables across different patient groups (including age, race, sex), and across the study arms as well as overall and by sites.

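### The end-of-shift rule allows scores taken long before departure to be stored as ED Discharge scores, and no rule uses the in-window Post score of patients who leave soon after it

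*Combined protocol and SAP*

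**What the plan says.** Section 6.2.4 states that the ED Discharge assessment "will be obtained within 15 minutes of" the patient's discharge, in both arms. The same paragraph adds two operational rules.

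- **Shift end.** If the staff member's shift is over and more than 15 minutes have passed since Post, "study staff will collect discharge scores from the participant and leave for the day".
- **Early leavers.** "Discharge scores will not be attempted to be collected if the participant is discharged within 15 minutes of when post treatment scores were collected". The text continues: "This will not be considered missing data".

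Two results depend on this assessment. Section 9.5 lists among the primary outcomes "pain intensity change scores for Pre-Treatment to Post-Treatment and Pre-treatment to ED Discharge", and the table in section 6.1 stars discharge pain as a primary assessment. Section 9.5 also says "we will also track completeness of data collection, and patterns and proportions of missing data at each time point", and section 9.5.1 says "Data collection forms collected at each time point will be evaluated for quality and completeness".

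Section 9.3 (populations) is marked not applicable. The discharge forms in Appendix B hold pain, anxiety, satisfaction and, for acupuncture, ED impact. They have no shift-end flag and no time item. The EHR extract described in section 10.2 does not name discharge time.

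**The concern.** The shift-end rule contradicts the definition it follows. A score taken 20 minutes after Post, from a patient who stays for hours more, is stored under the same name as a score taken at the door. This is foreseeable. Section 6.2.1 has teams "staffing an average 2.5, 4-6 hour recruitment/intervention sessions per week". Pre may come about an hour after rooming and Post about an hour after Pre (sections 6.2.2 and 6.2.4), so patients enrolled late in a session will often still be in the ED when staff leave.

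Two things are at stake. Completeness by time point is a feasibility result meant to inform the definitive trial, and a count that includes out-of-window scores overstates how often a true discharge score can be obtained. The Pre-to-Discharge change would also blend two time points. That blend could differ by arm, because pain medication in the acupuncture arm waits until after the session (section 5.3.3), so a score soon after Post would catch less of its effect there.

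The early-leaver rule raises a different problem. Those patients hold a Post score that already meets the 15-minute window, yet nothing says it is used. Without such a rule they are absent from the change summary, and leaving early is a post-randomisation event.

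**Working it through.** **The plan's own figures.** The documents give no figure for discharge completeness in this trial and no frequency for either rule, so there is nothing to reproduce on this point. The one power-based figure, in section 9.2, does reproduce. The pooled SD is √((2.52² + 3.2²)/2) = 2.880. Then 2 × (2.880 × (1.645 + 0.842)/0.65)² = 242.8 per arm; × π/3 for the Mann-Whitney test = 254.2, so 255 per arm and 510 in total; 255/0.78 = 326.9, so 327 per arm and 654 in total. It does not use the discharge score and is unaffected.

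**Completeness.** Inputs: N = 150 (section 9.2). Assumed: 22% with no score (33 patients, the complement of the pilot's roughly 78% in section 2.2), 10% leaving within 15 minutes of Post (15 patients), and a share e with an out-of-window shift-end score. In-window discharge scores = 150 − 33 − 15 − 150e. Early leavers are counted as complete in both right-hand columns.

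| e | Shift-end | In-window discharge | Complete as the rules allow | In-window, Post carried |
|---|---|---|---|---|
| 0% | 0 | 102 | 117/150 = 78% | 117/150 = 78% |
| 10% | 15 | 87 | 117/150 = 78% | 102/150 = 68% |
| 20% | 30 | 72 | 117/150 = 78% | 87/150 = 58% |
| 30% | 45 | 57 | 117/150 = 78% | 72/150 = 48% |

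Each 10% adds 10 points. The exact 95% interval for 117/150 is 70.5 to 84.3%, which excludes 68%, so the planned interval would not reveal the gap even at e = 10%.

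**Early leavers and the denominator (e = 10%).**

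- Shift-end scores accepted: early leavers counted as complete, 117/150 = 78.0%; left out of the denominator, (87 + 15)/135 = 75.6%.
- Shift-end scores rejected: 102/150 = 68.0% against 87/135 = 64.4%.

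Leaving early leavers out gives the lower figure both times.

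**Change score.** Pilot reductions (section 2.2), acupuncture minus usual care: at 60 minutes 3.00 − 1.56 = 1.44; at discharge 2.71 − 2.53 = 0.18. If a share s of discharge scores is shift-end and resembles Post in both arms, the apparent discharge difference is (1 − s) × 0.18 + s × 1.44:

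- s = 10%: 0.162 + 0.144 = 0.31
- s = 20%: 0.144 + 0.288 = 0.43
- s = 30%: 0.126 + 0.432 = 0.56

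**Precision of those inputs.** Assume 0.78 × 23 ≈ 18 per arm, so t on 34 df is 2.03. The half-width at 60 minutes is 2.03 × √((2.51² + 2.37²)/18) = 1.65; at discharge it is 2.03 × √((1.86² + 2.27²)/18) = 1.41. The pilot differences are therefore 1.44 ± 1.65 and 0.18 ± 1.41.

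**The case against.** The shift-end rule is openly stated and practical. With sessions of 4 to 6 hours, the alternative is often no later ED score at all, and section 9.5 already commits to tracking missing-data patterns. This stands as a reason to keep collecting these scores. It does not justify storing them unmarked under a definition they may not meet.

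Three stronger readings are tempting, and the documents do not support them.

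- A reader might infer that not counting early leavers as missing inflates completeness. Their Post score lies inside the 15-minute window, so treating them as not missing is defensible. The text does not take them out of any denominator, and the check above shows that doing so would lower the figure relative to counting Post as complete.
- A reader might infer that a between-arm discharge comparison is biased. None is specified. Section 9.5 plans descriptive summaries of the change score overall, by site and by demographic group. Sections 3 and 9.5.1 centre the primary outcome on recruitment, retention and data completeness.
- A reader might take the 0.18-to-0.56 series as an estimate of bias. The shares are assumed, the rule permits scores well after Post as well as soon after it, and the pilot differences carry wide intervals.

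REDCap may also time-stamp entries automatically, but the documents do not say so, and score times alone would not give the interval to discharge.

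**Conclusion.** The point holds as a contradiction between a definition and a collection rule in one paragraph, with no flag, time item, denominator rule or sensitivity summary to offset it. It can overstate in-window discharge completeness, point for point with the share of randomised patients whose shift-end score falls outside the window, and it can mix time points in a descriptive change score that section 9.5 calls primary. Whether it does so materially cannot be known from the documents. The 0 to 30% shift-end shares, the 10% early-leaver share and the likeness of shift-end scores to Post are all assumptions. A shift-end score that proves to fall within 15 minutes of discharge does no harm.

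The early-leaver gap is smaller and separate: an unstated use of Post that leaves the change summary selected on a post-randomisation event.

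**What to change.** Amend sections 6.2.4 and 9.5 as follows.

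- **(a)** When discharge falls within 15 minutes of Post, use the Post score as the discharge score and count it as complete. The Post forms in Appendix B hold the same items as the discharge forms, so nothing is lost.
- **(b)** Record the score time and the actual discharge time, and flag shift-end scores. Count as in-window any that prove to lie within 15 minutes of discharge.
- **(c)** Report counts of in-window, Post-carried, out-of-window shift-end and missing discharge scores, by arm and site, over all randomised patients.
- **(d)** Summarise Pre-to-Discharge change with and without the out-of-window shift-end scores.

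The cost is protocol wording, one flag and the time fields. No data are discarded and no sample size changes. Reported in-window completeness may come out lower.
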